16.1.2. Best Overall Response

Best overall response (BOR) will be calculated based on the overall visit responses obtained up until RECIST progression is documented, irrespective of whether patients discontinued study medication. In the absence of RECIST progression, BOR is determined by using visit responses up until the last evaluable overall visit response.

Note, CR or PR response(s) after receiving subsequent anti-cancer therapy will not be included.

A patient's overall best objective response will be determined:

- CR: At least one visit response of CR confirmed by subsequent imaging at least 25 days (4 weeks – 3 days window) later with no evidence of progression between confirmation visits. It is required that there is no other overall response, except CR and NE, between the first CR and the subsequent confirming CR which meet the confirmed CR criteria, i.e. CR-NE-CR is the confirmed CR.
- PR: At least one visit response of PR confirmed by subsequent imaging at least 25 days (4 weeks – 3 days window) later with no evidence of progression between confirmation visits. It is required that there is no other overall response, except CR or PR or NE, between the first PR and the subsequent confirming CR or

CCI

PR which meet the confirmed CR or PR criteria, i.e PR-NE-PR is the confirmed PR. If the first PR followed by SD and no matter the requirement of SD is satisfied or not, i.e. PR-SD-PR, the subsequent PR will not be qualified as confirmed PR.

- SD needs to sustain for at least 8 weeks: Stable disease recorded at least 53 days after start of treatment (8 weeks from start of treatment, and also allowing a 3-day visit window). For example, an overall visit response of SD on day 28 will not be considered as SD.
- PD: Progression, or death in the absence of CR/PR or SD.
- NE: No evidence of CR/PR or SD or PD or death.
- Unconfirmed CR: If the BOR is not qualified as confirmed CR or PR but with at least one visit response of CR prior to subsequent new anti-tumor therapy or PD, then it will be considered as unconfirmed CR.
- Unconfirmed PR: If the BOR is not qualified as confirmed CR or PR but with at least one visit response of PR prior to subsequent new anti-tumor therapy or PD, then it will be considered as unconfirmed PR.

In addition, following special scenarios shall be considered for the determination of BOR:

- If a patient receives new anti-tumor therapy(s), for that patient, tumor assessments after the first new anti-tumor therapy (same day inclusive) will be considered inadequate, thus not counted towards the determination of BOR.

The table below illustrates the derivation of BOR (with confirmed response) and BOR (regardless of confirmation). Category of confirmed response is dependent on response at the subsequent time-point, and whether the minimum duration criterion for SD has been satisfied.

Overall Response at First Time-point	Overall Response at Subsequent Time-point	SD Sustaining Duration Met at First Time-point	BOR Based on the Two Visits	BOR Regardless of Confirmation (for Unconfirmed CR or PR)
CR	CR	Yes/No	CR	CR
CR	PR	Yes/No	SD/PD	CR (Unconfirmed)
CR	SD	Yes/No	SD/PD	CR (Unconfirmed)
CR	PD	Yes/No	SD/PD	CR (Unconfirmed)

CR	NE	Yes/No	SD/NE	CR (Unconfirmed)
PR	CR	Yes/No	PR/PR	PR
PR	PR	Yes/No	PR	PR
PR	SD	Yes/No	SD/SD	PR (Unconfirmed)
PR	PD	Yes/No	SD/PD	PR (Unconfirmed)
PR	NE	Yes/No	SD/NE	PR (Unconfirmed)
NE	NE	Yes/No	NE	NE

CR = Complete Response; NE = Not Evaluable; ORR = Objective Response Rate; PD = Progressive Disease; PR= Partial Response; SD = Stable Disease.

For patients who progress and subsequently have a response, then the best objective response is only derived from assessments up to and including the time of the progression (i.e., it will not include the response after the patient has progressed).

Tumor response data for dosed patients that had non-measurable disease at baseline (i.e. did not meet study inclusion criteria 7) will be flagged and reviewed according to procedures described in Appendix 3 of the protocol.

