5.1.2 Dose Expansion Phase

The expansion phase will evaluate the anti-cancer activity of surufatinib, and confirm the safety and tolerability of surufatinib at the RP2D determined at the end of the dose escalation phase.

Under amendment 7 of this protocol, the MTD was declared when 2 of the 6 DLT evaluable patients in Cohort 7 (400 mg QD dose) of the dose escalation phase reported DLTs. There was an ad hoc meeting of the SRC on 30 November 2018. The SRC agreed with the declaration of 300 mg QD as the MTD of surufatinib in this trial and agreed that 300 mg QD is the RP2D going forward. The minutes of this ad hoc SRC meeting were distributed to all investigative sites on the same day. It was also agreed that patients who were already receiving 400 mg QD could remain on this dose, provided that 1) there was no major toxicity and 2) the affected patients gave informed consent not to reduce the dose to 300 mg after discussion with the investigator. However, no patients could have their dose escalated to 400 mg going forward, including all patients in the dose expansion phase.

The safety of all enrolled patients will be closely monitored from the time of the initial dose of investigational treatment until 30 days after the last treatment dose. Any SAEs that occur after the informed consent form (ICF) is signed, but before the first dose of study drug is taken, should also be reported. All AEs will be graded in accordance with the NCI CTCAE v. 4.03. Tumor assessments will be conducted according to RECIST Version 1.1 criteria at screening, Cycle 2 Day 1 and every 8 (± 1) weeks thereafter. Confirmation of

CR and PR is required at no less than 4-week intervals between the date of initial response/progression and the confirmation assessment date.

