8.2 Efficacy Assessments

8.2.1 Tumor Assessment

All measurable lesions should be assessed and documented at screening and re-assessed at each subsequent tumor evaluation (see [Appendix 1](#)). Response assessments will be performed by the investigator using physical examination and image-based evaluation.

Screening assessments include CT scans with oral or IV contrast (unless contraindicated) of the chest, abdomen, and pelvis. MRI scans are allowed if CT contrast is contraindicated. Bone scans and CT scan of neck should also be performed if clinically indicated. The same radiographic procedure used to define measurable or non-measurable lesions at baseline must be used throughout the study for each patient. At the investigator's discretion, CT scans may be repeated at any time if progressive disease is suspected.

Disease status will be assessed using RECIST Version 1.1 (see [Appendix 3](#)). At the investigator's discretion, other methods of assessment of measurable disease as per RECIST Version 1.1 may be used. Confirmation of CR and PR is required at no less than 4-week intervals between the date of initial response/progression and the confirmation assessment date.

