10.6.2 Secondary Efficacy Endpoints

- ORR, defined as the proportion of patients with a best overall response of complete response (CR) and partial response (PR) per RECIST Version 1.1. To be assigned a status of PR or CR, changes in tumor measurements must be confirmed by repeat assessments performed no less than 4 weeks after the criteria for response are first met.
- DCR, defined as the proportion of patients with best overall response of CR, PR, or SD per RECIST Version 1.1.
- TTR, defined as the time between the start date of study drug until first documented response (CR or PR) according to RECIST Version 1.1.
- DoR, defined as the time from the first time that the objective response reaches CR or PR, whichever comes first, until the occurrence of PD or death (if the death of the patient occurs before recording the PD).
- Percent changes of tumor size from baseline of target lesion will be calculated at each visit, and the maximum percent per patient will be selected. Waterfall plots will be used to depict the tumor shrinkage in target lesion. These plots will display the best percentage change in target lesion size.

ORR and DCR will be estimated and 95% exact CIs based on the Clopper-Pearson method will be presented. The time to event endpoints, TTR and DoR will be described in tabular and graphical format using Kaplan-Meier method, including estimated median (in months) with 95% CI, 25th and 75th percentiles.

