16. EFFICACY OUTCOMES

Efficacy data will be summarized by dose cohort in dose escalation phase and by disease cohort in dose expansion phase. PFS and OS will be analyzed for the SAS. The other efficacy variables (BOR, ORR, DCR, TTR, and DOR) will be analyzed for EAS.

Treatment efficacy will be evaluated by using tumor responses which will be assessed and documented at Screening, Day 1 of Cycle 2 and every 8 (+/-1 week) weeks on Day 1 of every other cycles afterwards (i.e. Cycle 4, 6... etc), until the occurrence of progressive disease (PD) according to the standard of Response Evaluation Criteria in Solid Tumors (RECIST) Version 1.1. Confirmation of CR and PR is required at no less than 4-week intervals between the date of initial response/progression and the confirmation assessment date. When the patient interrupts study medication due to AEs or other reasons, the evaluation should be conducted as scheduled. For suspected cases of PD before the start of the next scheduled assessment, additional tumor assessments will be done.

Tumor responses data are captured on CRF page "Tumor Measurement - Target Lesions", "Tumor Assessment - Non-Target lesions", "Tumor Assessment - New Lesions" and "Assessment of Disease". The confirmed best overall response (BOR, refer Section 16.1.2) will be summarized for EAS and will be presented together with summaries for objective response rate (ORR) and disease control rate (DCR).

The baseline sum of diameters will be presented with other baseline characteristics.

Tumor assessments for target lesion, non-target lesion, and new lesion will be presented in a listing. In addition, a listing of overall response including lesion responses, sum of diameters, and the corresponding change from baseline in tumor diameter will be provided.

Tumor assessment performed at the treatment completion visit (details can be found in SAP Section 7.3) is an eligible data point for the derivation of all efficacy endpoints, following the derivation rules described in Section 16.1.

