16.1.3. Objective Response Rate

Objective response rate (ORR) is defined as the proportion of patients with a best overall complete response (CR) or partial response (PR) per RECIST V.1.1. To be assigned a status of PR or CR, changes in tumor measurement must be confirmed by repeat assessment performed no less than 4 weeks after the criteria for response are first met. ORR (regardless of confirmation) will also be computed separately, including in the numerator subjects who have CR, unconfirmed CR, PR or unconfirmed PR. The denominator for the calculation of ORR and ORR regardless of confirmation will include all patients in EAS.

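### SAP 16.1.2 confirms responses at 25 days, while the protocol and the rest of the SAP require at least 4 weeks, and SAP 4.4 does not declare the relaxation

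*SAP*

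**What the plan says.** SAP 16.1.2, which derives BOR, treats a CR or PR as such when it is "confirmed by subsequent imaging at least 25 days" later, a figure that it explains as 4 weeks less a 3-day window.

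SAP 16.1.3 sets a different floor for the same status: changes in tumor measurement "must be confirmed by repeat assessment performed no less than 4 weeks after the criteria for response are first met". Protocol 10.6.2 has the same rule: "must be confirmed by repeat assessments performed no less than 4 weeks after the criteria for response are first met". Protocol 8.2.1 states it for tumor assessment generally: "Confirmation of CR and PR is required at no less than 4-week intervals". Protocol 5.1.2, SAP 4.1.2 and the opening text of SAP 16 repeat that minimum. None of these six places gives a window.

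Two further statements fix how ORR relates to BOR. SAP 16.1.3 has ORR "defined as the proportion of patients with a best overall complete response (CR) or partial response (PR) per RECIST V.1.1", and SAP 16 says: "The confirmed best overall response (BOR, refer Section 16.1.2) will be summarized for EAS and will be presented together with summaries for objective response rate".

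SAP 4.4, the section for changes from the protocol, lists only additional ECG analyses.

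**The concern.** One section of the SAP uses a shorter confirmation interval than every other place that states one, protocol included. The 4-week rule is a floor on the gap between two assessments. It is not a target date with a tolerance on either side, so subtracting a visit window changes the criterion.

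At stake is which patients count as confirmed responders. ORR is a secondary endpoint in both phases. TTR (SAP 16.1.5) and DoR (SAP 16.1.6) are restricted to confirmed responders and inherit whichever rule is programmed. A clinical study report that quotes the protocol's definition of ORR but computes it with the 25-day rule would misdescribe its own result. SAP 5.2 says that pNET and epNET efficacy was analysed in support of a regulatory submission, so the definition in those arms should admit one reading.

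**Working it through.** **Inputs.** The 25-day rule and the 53-day stable-disease rule are in SAP 16.1.2. The 4-week minimum is in SAP 16.1.3 and the other places listed above. The scan schedule (Cycle 2 Day 1, then every 8 ± 1 weeks) is in SAP 16, and the ± 1-day visit window for Cycles 1 and 2 in SAP 7.5. The treatment completion visit falls 30 ± 7 days after the last dose (SAP 7.3), and its scan is eligible for all efficacy endpoints (SAP 16). Planned cohort sizes are in Protocol 10.1. Gaps are plain differences between scan dates.

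**1. The plan's own figure.** 4 × 7 − 3 = 25 days. The parallel SD rule also reproduces: 8 × 7 − 3 = 53 days. The 25 is intended and is not an arithmetic slip.

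**2. Where the rules differ.** 4 × 7 = 28 days without a window. The rules part company only at gaps of 25, 26 or 27 days.

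**3. Which scans can fall there.** Two consecutive scheduled scans, the first a week late and the second a week early, are 56 − 7 − 7 = 42 days apart. From Cycle 2 Day 1 (one day late) to the next scan (a week early) is 56 − 1 − 7 = 48 days. Scheduled scans therefore never reach the disputed zone. An unscheduled scan can. So can a treatment completion scan, due 23 to 37 days after the last dose, if dosing stops near the date of first response.

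**4. A 25–27 day scan is not sufficient.** SAP 16.1.2 does not require the confirming scan to be the next one. For PR, further CR, PR or NE assessments may intervene. Illustrative sequences, in days from first response:

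| Sequence | At least 25 days | At least 28 days |
|---|---|---|
| PR 0, PR 26, PR 56 | confirmed | confirmed |
| PR 0, PR 26, PD 56 | confirmed | not confirmed |
| PR 0, PR 28, PD 56 | confirmed | confirmed |

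Only the second pattern changes status: an off-schedule scan at 25 to 27 days and no later qualifying CR or PR before progression or new therapy.

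**5. Size per affected patient.** The shift in ORR is 100/n points, with n the EAS size, assumed equal to planned enrolment:

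- pNET or epNET: 100/15 = 6.7 points
- BTC: 100/30 = 3.3 points
- STS: 100/55 = 1.8 points

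As an illustration at n = 15, 3 responders give 20.0% (exact 95% CI 4.3 to 48.1) and 2 give 13.3% (1.7 to 40.5). One reclassified patient is visible in the point estimate but small against the interval.

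**6. DCR.** In the SAP 16.1.2 table an unconfirmed CR or PR generally becomes SD once the SD duration is met, and SD counts towards DCR. If the first response is at or beyond 53 days, DCR does not move. If it is at Cycle 2 Day 1 (study day 29), the repeat scan falls at about day 29 + 25 = 54 to 29 + 27 = 56, about the point where the 53-day SD minimum is reached. Only a literal use of the table column that tests SD duration at the first time point could cost the patient disease control.

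**The case against.** The best defence is that 16.1.2 is the working version of the 4-week rule. It shows its derivation openly, borrows the 3-day visit window that SAP 7.5 and Protocol 8.3.2 use elsewhere, and applies the same allowance to SD. ORR is defined from BOR, 16.1.2 is the only BOR derivation, and SAP 16 presents the two together by reference to it. Programmed that way, the outputs agree.

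Much of this stands. A reader might infer that the same table will show a confirmed BOR and a confirmed ORR that contradict each other. The documents do not support that as the expected result, because ORR follows naturally from the 16.1.2 BOR. The likelier fault is an ORR that agrees with BOR but not with its own written definition.

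Three other inferences also go too far:

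- That every response re-scanned at 25 to 27 days is affected. A later qualifying scan confirms it under either rule.
- That DCR is materially exposed. Most reclassified responders would still count as SD.
- That one patient moves a reported STS-subtype ORR by 10 points (1/10). Protocol 10.6 and SAP Appendix 1 present STS as one arm, and Protocol 10.3 only allows that some subtype summaries may be given.

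The defence does not remove the contradiction. A window for attending a visit does not lower a stated minimum between two scans. Six other places give that minimum without a window, and SAP 4.4 does not record the departure.

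**Conclusion.** The inconsistency is real and minor. SAP 16.1.2 relaxes the confirmation interval by 3 days against the protocol and the SAP's other statements, without declaring it. If ORR is built on that BOR, confirmed ORR and the TTR and DoR responder sets depart from the stated definition for any patient who meets both conditions in step 4 of the working.

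The per-patient shifts in ORR, from 1.8 to 6.7 points by arm, rest on the EAS equalling planned enrolment. The EAS also requires a post-baseline tumor assessment, so it may be smaller and the shift per patient slightly larger. The documents give no frequency, and the number affected could be zero. The primary PFS rates and ORR regardless of confirmation do not depend on the interval, and the study has no formal hypothesis testing. This is a matter of definition and reporting and does not threaten the main conclusions.

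**What to change.** State one confirmation interval throughout. The simpler route is to change 16.1.2 to at least 28 days for CR and PR, which matches the protocol and SAP 4.1.2, 16 and 16.1.3. No information is lost: earlier re-scans stay in the unconfirmed CR and PR categories that 16.1.2 already defines, and they count in ORR regardless of confirmation.

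If the sponsor intends 25 days, put that figure in SAP 16.1.3, 16 and 4.1.2 and declare it in SAP 4.4 as a change from the protocol.

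The cost is one number in the SAP and in the BOR program for the first route, or a few lines of SAP text for the second. A short listing of CR or PR patients whose only confirming gap is 25 to 27 days would show whether any reported figure changes.

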5.6 Overall Survival Follow Up

Overall survival is defined as the time from the date of the first dose of study drug until the date of patient death (any cause). Investigators and/or delegated site staff should follow patients enrolled to the BTC and STS expansion cohorts, who have signed informed consent under sponsor Amendment 8 (or later), until death or until the patient is lost to follow up. Follow up for OS will begin after the end of treatment (EOT) visit has been completed. Patients should be followed every 8 weeks (\pm 2 weeks) via telephone or in a manner that follows local site SOPs. Site staff should attempt to contact a patient 3 times and consult with authorized family members for the status of the patient (when applicable) before considering a patient lost to follow up. Data to be collected should include the date the patient was last known to be alive, the date of death, and the cause of death.

Treatment completion of patients will occur if any of the following 3 criteria is met:

1. Disease progression (according to RECIST Version 1.1), unless there is reasonable evidence of clinical benefit to justify continuation on the study drug. The continuation decision should be made by the investigators in consultation with the sponsor. The disease progression date is the date when radiological disease progression is first reported according to RECIST Version 1.1 criteria;
2. Death;
3. End of this study.

Early discontinuation of study drug will occur if any of the following criteria is met:

1. Patient withdrawal of informed consent;
2. Intolerable toxicity;
3. Poor patient compliance;
4. Use of other antitumor treatment during the study;
5. Pregnancy occurred during the study treatment period;
6. Patient is lost to follow-up;
7. Treatment discontinuation is in the best interest of the patient based on the assessment of the investigator and sponsor.

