Documented progression before start use of new anti-tumor therapy and no two consecutive missed tumor assessment visits	Event	Date of documented disease progression
Death without progression and without use of new anti-tumor therapy and without missing two consecutive tumor assessment visits	Event	Date of death
Death or progression after two or more consecutive missed tumor assessments	Censor	Date of last evaluable tumor assessment prior to the consecutive missed tumor

CCI

		assessment visits
No evaluable baseline or post-baseline tumor assessment and no new lesion found and no death within two scheduled tumor assessment visits post-baseline	Censor	Date of first dosing of study medication
New anti-tumor therapy started prior to documented disease progression or death on study	Censor	Date of last evaluable tumor assessment before start use of new anti-tumor therapy
No progression and no death before end of study or data cut-off	Censor	Date of last evaluable tumor assessment

Note: Symptomatic deterioration will not be regarded as a progression event.

The PFS will be programmatically derived as follows:

1. If a patient had disease progression or death, then

$PFS \text{ (month)} = ([\text{date of earliest evidence of disease progression or death (including death from any cause)} - \text{start date of study medication}] + 1) / 30.4375$; Otherwise,

2. If the patient was known to have developed one of above censoring criteria, then the PFS is censored and

$PFS \text{ (month)} = ([\text{date of censoring} - \text{start date of study medication}] + 1) / 30.4375$.

3. Special scenario such as two or more consecutive missing tumor assessment visits or new anti-cancer treatment will be handled according to the rules provided in Table 1.

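### The BOR rule counts a death at any time as PD, so the PD/NE split can contradict a censored PFS and depends on whether the death was captured

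*SAP*

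**What the plan says.** **BOR categories (SAP 16.1.2).** The two lines at issue are "PD: Progression, or death in the absence of CR/PR or SD" and "NE: No evidence of CR/PR or SD or PD or death". SD must be "Stable disease recorded at least 53 days after start of treatment", and the section adds that "an overall visit response of SD on day 28 will not be considered as SD".

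**Limits on BOR data (SAP 16.1.2).** Without RECIST progression, "BOR is determined by using visit responses up until the last evaluable overall visit response". After a switch of treatment, "tumor assessments after the first new anti-tumor therapy (same day inclusive) will be considered inadequate, thus not counted towards the determination of BOR". A separate note drops CR and PR responses seen after subsequent therapy. None of these mentions deaths.

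**PFS (SAP 16.1.1, Table 1).** A death counts as an event only without new therapy and without two consecutive missed assessments, a window set at 126 days. Censoring at the last evaluable scan applies to "New anti-tumor therapy started prior to documented disease progression or death on study". The missed-visit, no-evaluable-scan and new-therapy rules are introduced as applying to PFS alone.

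**Capture of deaths.** Protocol 5.6 follows survival "until death or until the patient is lost to follow up", but only in the BTC and STS expansion cohorts and only for consent under Amendment 8 or later. In all arms, Protocol 9.12 records deaths in the AE reporting period. That period runs to 30 days after last dose in Protocol 9.3 and to 37 days in SAP 17.1, or to study discontinuation or termination if later. After a stop without progression, Protocol 5.5 continues scans until progression, new therapy or withdrawal of consent.

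**The concern.** A patient with one stable scan at Cycle 2 Day 1 belongs to the Efficacy Analysis Set (SAP 6.4) but has no qualifying SD. If no later scan counts, the presence or absence of a recorded death alone decides between PD and NE. The rule does not ask whether the death came two weeks or a year later, or whether another treatment had started.

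Two things follow:

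- The same record can be PD in the BOR table and censored without progression in the PFS listing.
- The category depends on how long deaths were sought. It can therefore differ between patients with the same tumor course, and it can move from NE to PD between data cuts with no new tumor data.

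Confirmed BOR is presented together with ORR and DCR (SAP 16). A reader of its PD row would take it as tumor progression. SAP 16.4 plans no sensitivity analysis that would show the mixture.

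**Working it through.** **The plan's own figures.** The SD minimum is 8 × 7 − 3 = 53 days. The missed-visit window is 2 × (8 + 1) × 7 = 126 days. Both agree with the SAP. The first scheduled scan is Cycle 2 Day 1, about Day 29, which is too early for SD. The next is about Day 29 + 56 = Day 85.

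**Test patient (assumed).** One evaluable scan, SD on Day 29; last dose on Day 40; no later scan that counts. The 37-day reporting window ends on Day 40 + 37 = Day 77. A PFS time censored at Day 29 is 29 / 30.4375 = 0.95 months.

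| New therapy | Death | Gap from scan | BOR as written, death recorded | PFS, Table 1 | BOR with the fix |
|---|---|---|---|---|---|
| none | Day 60 | 31 days | PD | event, Day 60 | PD |
| none | Day 155 | 126 days | PD | event, Day 155 | PD |
| none | Day 156 | 127 days | PD | censored, Day 29 | NE |
| Day 50 | Day 70 | 41 days | PD | censored, Day 29 | NE |
| Day 50 | Day 150 or 400 | 121 or 371 days | PD | censored, Day 29 | NE |

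Rows 1 and 2 show no conflict. Rows 3 to 5 do: row 3 because the gap exceeds 126 days, rows 4 and 5 because new therapy came first.

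**Effect of capture.** Deaths on Days 60 and 70 fall inside the reporting window and give PD in every arm. The deaths in the last row fall outside it and after tumor follow-up has ended. They are sought in a survival-followed BTC or STS patient (PD) but not in a pNET or epNET patient (NE if the death is not recorded). Deaths on Days 155 and 156 lie between: outside the window, but they may become known while scans are still due.

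The difference can also arise within an arm. Protocol 5.2 shows that Arm A already had patients on study at Amendment 7, so some BTC patients may not have consented under Amendment 8 or later. SAP 6 also pools escalation patients treated at the RP2D into the disease cohorts, and Protocol 5.6 does not follow them for survival.

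**Size per patient.** One patient moved between NE and PD shifts the PD row by 1/15 = 6.7 points, 1/30 = 3.3 points or 1/55 = 1.8 points at the planned arm sizes.

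**What does not move.** Neither PD nor NE enters the numerator of ORR or DCR, and their denominators do not depend on the PD/NE split. The PFS rates come from the separate rules in SAP 16.1.1.

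**The case against.** **The section already limits the data.** The sentence stopping BOR at the last evaluable visit response could be read as shutting out a late death. It limits visit responses, however, and a death is not one. Read as excluding deaths, it would empty the death clause. What stands is that the SAP is silent on death after new therapy; it does not say that such a death counts. Two programmers could produce different tables.

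**Few patients will qualify.** This stands. Stopping for toxicity is not enough, because scans continue under Protocol 5.5. SAP 16 also accepts a scan at the treatment completion visit. For a last dose on Day 40 that visit falls on Days 63 to 77 (30 ± 7 days later), so a stable result there would qualify as SD. It cannot do so where new therapy began on Day 50, because the scan is then disregarded.

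**PFS and BOR are different derivations.** True, and the SAP confines the PFS rules to PFS. That explains the mismatch but supplies no reason to call a much later death, after another treatment, progression on this one.

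**Little depends on it.** Also fair. There is no hypothesis testing, arms are summarized separately, and BOR is not itself a listed endpoint.

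**A stronger reading is tempting:** that nearly all such patients in the BTC and STS arms end as PD and almost none in the NET arms. The documents do not support it. Survival follow-up excludes earlier-consented patients and can end in loss to follow-up or at data cut-off. Deaths in the reporting window count in every arm, and the Death form in SAP 17.1.7 is not restricted by arm. Nor can a frequency be taken from the 15.8% stopping for TEAEs in Protocol 2.3. That figure covers stops at any time across studies, not stops before Day 53 without progression followed by a therapy switch or missed scans.

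**Conclusion.** The point holds as a minor defect of definition. As written, a recorded death without qualifying CR, PR or SD is PD whatever its timing and whatever treatment came between. The result contradicts censored PFS only when death follows new therapy or two consecutive missed assessments. It differs by arm, or within an arm, only when the death lies outside what was captured for some patients.

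The documents give no basis for the number of patients affected; it is probably small. The shift per patient is 6.7, 3.3 or 1.8 points at n=15, 30 or 55, taking planned enrollment as the denominator; the actual Efficacy Analysis Set may differ. Only the PD/NE split of the BOR table is at risk. A reader should not infer that response rates, disease control or the primary endpoints are biased by this rule.

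**What to change.** Replace the two category lines in SAP 16.1.2 with:

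- *PD: RECIST progression; or death with no qualifying CR, PR or SD, provided the death precedes any new anti-tumor therapy and is a PFS event under Section 16.1.1, Table 1.*
- *NE: every other patient without CR/PR, SD or PD, including those who die after new anti-tumor therapy or after two or more consecutive missed assessments.*

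BOR and PFS then agree in every row of the table above, and deaths found only through long survival follow-up after new therapy or missed assessments no longer alter BOR.

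The cost is two lines of text and one programming condition, with no new data. The downside is that a few more patients appear as NE.
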